6.5.1.4. Covariate analysis

The following baseline characteristics were studied by biomarkers in order to properly categorise the sample:

- Gender
- Age
- Primary Tumour location and sidedness (ascending colon, transverse colon, descending colon, sigma and rectum)
- Stage of the disease
- Surgery of the primary tumor
- ECOG Performance Status
- Number of metastatic organs
- Specific locations of metastasis including number, size and location node, lung, peritoneal and liver (considering also those patients with only resectable liver metastases for comparison)
- Mean values of haematological tests including leucocytes, haemoglobin, platelets,.
- Baseline LDH levels >450

- Mean ALP and Mean CEA
- Chemotherapy (FOLFOX+Cetuximab /FOLFIRI+Cetuximab)

These groups have been used for univariate and multivariable analysis in order to evaluate efficacy variables such as ORR and PFS. Disease response was clinically assessed by the investigator based on the radiological imaging data collected throughout the study. Any finding considered as non-assessable by the investigator was excluded from the analysis (it was considered as non-existent).

For continuous variables, mean, standard error (for efficacy variables), standard deviation (for other measurements), median, 25th percentile, 75th percentile, minimum and maximum, were evaluated. Categorical variables were presented using frequencies and percentages.

The 95% two-sided confidence intervals (95%CIs) of Kaplan–Meier quartiles for time to event variables were calculated according to Brookmeyer and Crowley methods (Brookmeyer, 1982). The 95% two-sided CIs for the Kaplan–Meier estimates at various time points were calculated according to the methods described by Collett (Collett, 1992).

Safety data were analysed throughout the entire study and presented by descriptive analysis.

6.5.1.5. Analysis of main study variables

The primary efficacy analysis of this trial was performed based on all subjects who provided their informed consents, were included in the trial, and did not present significant protocol deviations throughout the study period. .

Continuous and ordinal variables between independent groups were compared using the Wilcoxon rank-sum test and proportions were compared with Fisher's exact test. Clinical endpoints were ORR, DoR, PFS, and OS. Tumour assessments by CT scans were performed every 3 months until PD. Patients without a second CT scan evaluation were not assessable for ORR.

PFS was defined as the time of the signature of the ICF date until PD or death from any cause. Patients who did not experience PD or death were censored on the date of last examination. For more information regarding censoring see in Section 7.5.1.1. OS was defined as the time from the signature of the ICF date to death from any cause. Patients lost to follow-up or still in the study at database closure have been censored at the date last known to be alive.

Survival analyses including PFS and OS were performed using Kaplan–Meier methods. Cox proportional hazards regression with the Efron method for ties was used to identify prognostic factors for PFS and OS.

Multivariable analysis was performed using subject-matter knowledge and deciding a *priori* the variables to adjust by age (>65 years), sex, tumour site (right vs left), surgery of primary tumour, liver only metastases (<3 nodules and <5 cm vs >3 nodules or >5 cm), ECOG PS, LDH (>450 U/L) and CEA, BRAF mutational status, and type of therapy. This analysis was later adjusted by variables with p-values <0.10 in the

univariate analysis via the automated stepwise selection of variables (p-value for variable entry into the model was 0.2 and p-value to keep the variable in the model was 0.1).. All p-values were two sided.

The proposed sample size ensures establishing a consistent multivariable analysis. Clinical variables and biomarkers were used to build scores intended to predict 12- months PFS as following:

1. A multivariable Cox model was built with those clinical variables that in the univariate analysis had a p-value ≤ 0.15 (PS, chemo regimen, sidedness, resectable liver metastases).
2. A score was established for each patient by adding up the regression coefficients of the multivariable Cox model present in these patients. If for example PS>0 was a negative predictor for PFS (i.e. regression coefficient is negative; e.g. -0.5) and left side tumour was a positive prognostic factor (regression coefficient was positive, e.g. 0.6) then for a patient with PS>0 and left sided tumour the two scores were added (-0.5 + 0.6=0.1). If a patients has PS=0 then the score to be added is 0, as it is the case for right sided tumour in the example.
3. Using a logistic regression model for the outcome 12-months PFS, a ROC curve was computed to choose the score cut point that classifies most patients correctly 4. Patients were dichotomized according to that cut point.
5. Steps 2 to 4 were repeated, adding each of the three biomarkers.
6. Definition of the discriminating power of the 4 scores for prognosis of or 12-months PFS according to these results were compared via ROC curves.
7. Determination of the most suitable score for 12-months PFS according to these results.

The four scores included in the first multivariate model using clinical factors where PS>0, chemotherapy with FOLFIRI and cetuximab, left sided and resectable liver metastases were considered (Score 1). The additional scores considered the four clinical factors above plus the status of each biomarkers (Score 2: BRAF mutation; Score 3: PI3K mutant or PTEN ≤ 3) and Score 4: Double-positive Phenotype (DP).

All analyses were performed using SAS V9.3 (SAS Institute, Cary, NC, USA) statistical software.

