10.2.2 Secondary endpoints

Objective response rate (ORR): incidence of a CR or PR according to the revised RECIST 1.1 criteria.

Duration of response (RD): (calculated only for subjects having an objective response) time from first objective response to progression of radiological disease according to the revised RECIST 1.1 criteria. For subjects who present a response and have not had progression, the duration of the response will be censored on the last assessment date of the evaluable disease.

Overall survival (OS): Time elapsed from the date of inclusion to the date of death. For subjects who have not died or who have been lost to follow-up by the data analysis cut-off date, the SG will be censored on the date of the last contact.

Safety: Type, frequency, intensity of adverse events related to the combination treatment.

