10.3 General considerations

The primary endpoint and secondary efficacy endpoints will be analyzed using the ITT analysis group and the per-protocol analysis group.

Efficacy analyzes will be based on radiographic images collected during the study and analyzed by the investigator. Any examination that the investigator classifies as not evaluable will be omitted from the analysis (it will be considered as no examination).

For continuous variables, the mean, standard error (for efficacy variables) or standard deviation (for other measurements), median, 25th percentile, 75th percentile, minimum, and maximum will be provided. For discontinuous data, the frequency and percentage distributions will be provided. The two-sided 95% confidence intervals of the Kaplan-Meier quartiles will be calculated using the methods described by Brookmeyer and Crowley (Brookmeyer, 1982). Two-sided 95% confidence intervals for the Kaplan-Meier rates at specific time points will be calculated using the methods described by Collett (Collett, 1992).

Safety data will be analyzed throughout the study.

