6.5.1.2. Secondary endpoints

- Serum and tumor tissue secondary biomarkers evaluated to predict acquired chemo-resistance including BRAF and PI3K.
- ORR was defined as the incidence of a complete or partial response according to the revised RECIST 1.1 criteria.
- DoR (calculated only for the subjects who present an Overall Response): Time from the first assessment of Overall Response to radiologically-confirmed PD according to the revised RECIST 1.1 criteria. For subjects who showed response and did not show progression, DoR was censored on the last date of assessable disease evaluation reported in the eCRF of the study.
- OS: Time from the signature of the ICF date to date of death. For subjects who did not die or were lost to follow-up on the closing date for data analysis, OS was censored on the date of last contact.
- Safety: Type, frequency, and intensity of AEs related to the combination treatment.

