6.5.1.3. Analysis population

Efficacy variables were analysed in all subjects who provided their informed consents, were included in the trial and did not present significant protocol deviations throughout the study period.

An intention-to-treat analysis in all patient enrolled into the study was not performed because the primary study objective was to evaluate the predictive value of the three biomarker BRAF, IGF-1RP/MMP-7 (Double-positive Phenotype/DP) and PI3K-PTEN on PFS in wt-RAS CRC patients receiving standard chemotherapy plus bi-weekly cetuximab as first-line therapy, but patients with significant protocol deviations (e.g. RAS mutations, missing biomarker data and those not receiving cetuximab treatment) could not contribute to the investigation of the primary objective.

All patients who received study medication were included in the safety analysis. .

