Pat. #	Hospital	Reason for exclusion from efficacy analysis	Valid for safety

Table 9. Response Rates (efficacy population) based on BRAF status

Best Response	N= all patients (%)	N= wt-BRAF (%)	N= mutant-BRAF (%)
Complete response (CR)			
Partial response (PR)			
Stable disease (SD)			
Disease Progression (PD)			
Not evaluable (NE)			
Overall response			
Disease Control Rate			

Figure 1. Progression free-survival

Progression free survival (PFS) based on the analysis of X patients showed a median of X (95% CI: X - X) months.

Figure 2. Overall survival

When OS was evaluated, an estimated median of X (95% CI: X - X months was reported.

The median OS of wt-BRAF patients was X (95% CI: X - X) months and for that of mutant BRAF patients was X (95% CI: X - X months (adjusted HR:X, CI 95% X- X; p-value=X).

Table 10. General toxicity profile (AEs+SAEs+SUSARs)

Adverse event	Any grade	Grade 3	Grade 4	Grade 5
	N (%)	N (%)	N (%)	N (%)

Table 12. Toxicity profile post treatment beginning (AEs+SAEs+SUSARs)

Adverse event	Any grade	Grade 3	Grade 4	Grade 5
	N (%)	N (%)	N (%)	N (%)

Table 13. Toxicity profile post treatment beginning related to treatment (AEs+SAEs+SUSARs)

Adverse event	Any grade	Grade 3	Grade 4	Grade 5
	N (%)	N (%)	N (%)	N (%)

Table 14. Toxicity profile post treatment beginning related to treatment with Cetuximab (AEs+SAEs+SUSARs)

Adverse event	Any grade	Grade 3	Grade 4	Grade 5
	N (%)	N (%)	N (%)	N (%)

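### The ORR denominator is unsettled: SAP 6.5.1.5 sets aside patients without a second CT, while the Table 9 shell appears to keep them in N as not evaluable

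*SAP*

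**What the plan says.** Both documents define ORR by its numerator only. Protocol 10.2.2 has "Objective response rate (ORR): incidence of a CR or PR according to the revised RECIST 1.1 criteria", and SAP 6.5.1.2 has "ORR was defined as the incidence of a complete or partial response according to the revised RECIST 1.1 criteria". Neither says who is in the denominator.

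On the analysis set, Protocol 10.3 plans: "The primary endpoint and secondary efficacy endpoints will be analyzed using the ITT analysis group and the per-protocol analysis group". The SAP drops the ITT analysis. Section 6.5.1.3 has "Efficacy variables were analysed in all subjects who provided their informed consents, were included in the trial and did not present significant protocol deviations", and its examples of significant deviations are RAS mutation, missing biomarker data and no cetuximab. A missing scan is not among them.

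SAP 6.5.1.5 then adds a rule specific to ORR: "Patients without a second CT scan evaluation were not assessable for ORR". The schedule beside it is "Tumour assessments by CT scans were performed every 3 months until PD", so if the baseline scan is the first CT, the second is due at about week 12.

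The Table 9 shell (SAP section 7) is headed as response rates in the efficacy population. It has columns for all patients, wild-type BRAF and mutant BRAF, and a best-response row that begins "Not evaluable (NE", listed with CR, PR, SD and PD.

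**The concern.** The sentence in 6.5.1.5 is the only rule in either document on how a patient without a post-baseline scan is handled for ORR. Read as an exclusion, it makes ORR conditional on reaching a second scan. Everyone it removes is someone for whom no response could have been documented, so the rate can only go up.

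ORR by marker is a secondary objective (SAP 5.2). SAP 6.5.1.4 also uses ORR in univariate and multivariable analyses, and 6.5.1.5 compares proportions with Fisher's exact test. Table 9 covers BRAF only; there is no response shell for PI3K-PTEN or the double-positive phenotype (DP), and none for the ORR models. For those analyses the 6.5.1.5 sentence is the only guide to whether such a patient is a non-responder or a missing value.

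**Working it through.** **Step 1. The two readings.**

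- *Exclusion.* The SAP uses similar terms elsewhere for things left out. In 6.5.1.4 a non-assessable finding is treated as non-existent; this concerns findings, not patients. In 6.5.2 the 155 patients become 170 to cover potentially non-assessable patients, who therefore do not count towards the 155.
- *Retention.* Table 9's title, its all-patients column and its not-evaluable row together imply that these patients stay in N and count as non-responders.

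**Step 2. Formula.** Let N be the efficacy population, R the responders and m the patients without a second CT. Taking baseline as the first CT, none of the m patients can be among the R.

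- Retained: ORR = R/N.
- Excluded: ORR = R/(N − m).
- Ratio of excluded to retained: 1/(1 − m/N), which is 1 when m = 0 and larger otherwise.

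**Step 3. Size.** The plan gives no ORR value, no ORR sample size and no m, so there is no figure of its own to reproduce. As an illustration I take 57.3% as the true ORR. Protocol 4.1 quotes this rate for cetuximab with FOLFIRI and for cetuximab with FOLFOX-4 in KRAS wild-type patients. The excluded shares are assumptions.

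| Share excluded | Calculation | Reported ORR | Change (points) |
|---|---|---|---|
| 0% (Table 9 layout) | 0.573/1.00 | 57.3% | 0 |
| 3% | 0.573/0.97 | 59.1% | +1.8 |
| 5% | 0.573/0.95 | 60.3% | +3.0 |
| 8% | 0.573/0.92 | 62.3% | +5.0 |
| 10% | 0.573/0.90 | 63.7% | +6.4 |

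In whole patients, with N = 181 (SAP synopsis) and an assumed R = 104, the retained rate is 104/181 = 57.5%. Excluding 5, 9 or 18 patients gives 104/176 = 59.1%, 104/172 = 60.5% or 104/163 = 63.8%.

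**Step 4. Marker contrast.** Group sizes are from SAP Table 6 (161 wild-type, 20 mutant BRAF). Responder counts of 97 and 8 are assumed.

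| Excluded (wild-type, mutant) | Wild-type ORR | Mutant ORR | Gap (points) | Fisher p |
|---|---|---|---|---|
| 0, 0 | 97/161 = 60.2% | 8/20 = 40.0% | 20.2 | 0.096 |
| 16, 2 (about 10% each) | 97/145 = 66.9% | 8/18 = 44.4% | 22.5 | 0.071 |
| 8, 4 (about 5% and 20%) | 97/153 = 63.4% | 8/16 = 50.0% | 13.4 | 0.295 |

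Equal missingness widens the absolute gap; clearly higher missingness in the mutant group narrows it. In the 20 mutant patients, excluding 3 would move 8/20 = 40.0% to 8/17 = 47.1%.

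**The case against.** The strongest reply is that the SAP never says these patients leave the denominator, and that the one place showing how ORR will be reported keeps them in. On Table 9's layout much of the remedy is already there and the inflation is zero. This stands, and it limits the point to a conflict between two parts of the SAP. It does not remove the conflict, because Table 9 does not extend to PI3K-PTEN, DP or the ORR models.

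A reader might also infer that those without a second CT are mainly early deaths, clinical progressions and toxicity withdrawals. The documents support this only in part. Symptoms of progression trigger an assessment at that time (Protocol 5.1 and the section on tumour response evaluation). Patients who stop for reasons other than progression are imaged at the safety visit (Protocol 8.4) and then every 12 weeks (Protocol 8.5). The baseline-only cases that Protocol 10.2.1 names are refusal to continue and loss to follow-up. Early deaths remain possible, since Protocol 6.1 admits ECOG 2 and a life expectancy of three months, but no count is given.

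Finally, ORR is secondary. PFS has its own event and censoring rules in SAP 6.5.1.1, and the ORR sentence plays no part in them.

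**Conclusion.** The point holds as an unresolved conflict over the ORR denominator. If 6.5.1.5 is applied as an exclusion, the bias is upward by 1/(1 − m/N): about 2 to 6 points for 3% to 10% excluded at an assumed ORR of 57.3%. If Table 9 governs, it is zero. The direction rests on counting the baseline scan as the first CT. The size rests on assumed values of ORR and m.

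Two stronger readings are tempting and not supported. One is that the reported ORR is inflated: this would need 6.5.1.5 to override Table 9, which the SAP does not say. The other is that marker differences are narrowed: the direction depends on missingness by group, which is unknown, and equal proportions widen the gap. What can be said is that with 20 BRAF-mutant and 23 DP patients, a handful of cases can shift a marker comparison.

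The SAP's omission of the protocol's ITT analysis is a separate matter. The denominator needs stating whichever set is used.

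**What to change.** Replace the sentence in SAP 6.5.1.5 with a rule of this form: ORR is CR plus PR divided by all patients in the efficacy population; patients without a post-baseline tumour assessment are classed as not evaluable and counted as non-responders in all ORR tables, tests and models.

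Report the number of not-evaluable patients, with reasons, by group for BRAF, PI3K-PTEN and DP. Show the evaluable-only ORR as a labelled secondary analysis, so that the effect of the rule is visible.

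The cost is one sentence and a few table rows, with no new data. The reported ORR may be slightly lower than under the exclusion reading.

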10.4 Analysis of the main variables of the study

The Cox regression analysis will be performed with the experimental biomarkers and the following prognostic variables (LDH, functional status, age, limited resectable disease (<3 nodules and <5cm). A classification will be performed using the most discriminatory variables. The classification It will be carried out with all the clinical variables of impact in the univariate analysis, including the 4 clinical variables (LDH, functional status, age, limited resectable disease (<3 nodules and <5 cm) and the 3 pathways previously described (BRAF, DP and PTEN). -PI3K) The classification will be carried out with the variables with the greatest impact in the multivariate analysis.

The proposed sample size ensures the construction of a consistent multivariate analysis.

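### The a priori Cox model in SAP 6.5.1.5 cuts age at 65 years and LDH at 450 U/L and gives no scale for CEA, so it adjusts somewhat less well than the recorded data allow

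*SAP*

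**What the plan says.** SAP 6.5.1.5 describes two separate pieces of modelling.

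- **The adjusted Cox model.** Its covariates are chosen beforehand. The list opens with "the variables to adjust by age (>65 years), sex, tumour site (right vs left), surgery of primary tumour" and ends with "ECOG PS, LDH (>450 U/L) and CEA, BRAF mutational status, and type of therapy". Age and LDH therefore enter as binary variables, and CEA enters in a form that is not stated. A further selection step follows: "This analysis was later adjusted by variables with p-values <0.10 in the" univariate analysis, by stepwise selection with entry at 0.2 and retention at 0.1.
- **The 12-month PFS score.** It starts from the clinical variables that in the "univariate analysis had a p-value ≤ 0.15 (PS, chemo regimen, sidedness, resectable liver metastases"). Score 1 holds these variables (the SAP synopsis leaves out regimen). Age, LDH and CEA are not among them.

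Protocol 10.4 names LDH, functional status, age and limited resectable disease as the clinical prognostic variables, with no cut for age or LDH. It does not list CEA. On how variables are combined it says only: "The classification will be carried out with the variables with the greatest impact in the multivariate analysis".

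The finer data exist. The source-verification schedule (SAP Table 3) includes date of birth and baseline LDH and CEA. SAP 6.5.1.4 lists age without a cut, LDH with the 450 cut, and "Mean ALP and Mean CEA". The cells of Table 6 for these variables are blank.

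**The concern.** A binary term treats a patient of 66 and one of 80 as equal, and puts a step between 65 and 66. When the true effect is gradual, part of the prognostic information is lost. If age or LDH also differs between biomarker groups, part of its effect stays in the biomarker hazard ratio. The results shell in SAP section 7 reports an adjusted hazard ratio for BRAF on overall survival, and this model is the natural source of it. At stake is the quality of adjustment for two variables that the protocol itself singled out, in a data set with small biomarker groups (20 mutant BRAF patients of 181 in Table 6).

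**Working it through.** The plan states no figure for the cost of these cuts, so there is none to reproduce. Its 115-event target does not depend on covariate coding.

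**1. Age cut at 65.** For a normal covariate with a linear log-hazard effect, the share of information kept by a cut with a proportion p above it is φ(c)² / [p(1−p)], where c is the cut in SD units.

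- Cut at the median: φ(0)² / 0.25 = 0.1592 / 0.25 = 0.637 (that is, 2/π). The loss is 36%, the smallest possible under normality.
- Assumed age means of 58 to 67 and SD of 9 to 11: losses run from 36% to 49%. Example: mean 62, SD 10 gives 38% of patients above 65 and a loss of 38%.
- Uniform age: the share kept is 3p(1−p), so p = 0.5 gives 0.75 (loss 25%) and p = 0.4 gives 0.72 (loss 28%).
- A true step at 65: no loss.

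**2. LDH cut at 450 U/L.** The same formula applies if log LDH is normal with a linear effect. The share of patients above 450 is not given. With 50%, 40%, 30% or 20% above the cut, the loss is 36%, 38%, 42% or 51%.

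**3. CEA.** It is not cut, so the formula above does not apply. If it were entered raw, were log-normal with SD s on the natural-log scale, and acted linearly on that scale, the large-sample share kept would be s² / (exp(s²) − 1). The loss is then 12% at s = 0.5, 42% at s = 1 and 73% at s = 1.5. Simulated trials of 181 patients (about 173 events) give smaller losses: about 13–17% at s = 1 and 31–47% at s = 1.5 to 2. If the effect is linear in raw CEA, nothing is lost. No single figure can be defended.

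**4. Effect on an adjusted biomarker hazard ratio.** Simulation with 181 patients, 20 of them biomarker-positive, and 300 runs per setting. Assumptions: age mean 62, SD 10; true biomarker HR 1.0; age shifted between biomarker groups by the amount shown.

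| Age HR per SD | Age shift (SD) | Continuous age | Age cut at 65 | No age term | SE of log HR |
|---|---|---|---|---|---|
| 1.2 | 0.3 | 1.031 | 1.052 | 1.091 | 0.269 |
| 1.2 | 0.5 | 1.020 | 1.052 | 1.120 | 0.264 |
| 1.5 | 0.3 | 1.011 | 1.058 | 1.136 | 0.234 |
| 1.5 | 0.5 | 1.017 | 1.093 | 1.215 | 0.237 |

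The excess from cutting ranges from ln(1.052/1.031) = 0.020 to ln(1.093/1.017) = 0.072 on the log scale, that is 0.07 to 0.30 of a standard error. The binary term removes 60–67% of the confounding that the continuous term removes; in the last row, ln(1.215/1.093) / ln(1.215/1.017) = 0.106 / 0.178 = 60%.

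**5. Effect on the benchmark, if age were in it.** Start from the reported AUC of 0.67. The binormal separation is d₁ = √2·Φ⁻¹(0.67) = 0.622. Adding an independent age term with odds ratio OR per SD gives AUC = Φ(√(d₁² + q·ln²OR) / √2), with q = 1 for continuous age and q = 2/π for age cut at its median.

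- OR 1.1: 0.672 continuous, 0.671 cut.
- OR 1.2: 0.677 continuous, 0.674 cut.
- OR 1.5: 0.700 continuous, 0.690 cut.

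The coding moves the AUC by about 0.001 to 0.010.

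**The case against.** The strongest reply is that the SAP's primary analysis (6.5.1.1) compares AUCs of scores, and the model with the age cut does not feed those scores. That is right, and it limits the point to the adjusted hazard ratios.

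A reader might infer that the same coding weakened the clinical benchmark and so flatters the biomarkers. The documents do not support this. Score 1 contains none of age, LDH or CEA. The synopsis says that all collected clinical variables were screened, so the three were candidates, but the form in which they were screened is not stated: 6.5.1.4 lists age uncut and 6.5.1.5 cuts it. The coding could have influenced which variables passed, but only for effects of some size. With an assumed age HR of 1.2 per decade, the chance of passing p ≤ 0.15 is about 81% continuous and 65% cut. At 1.05 per decade it is about 22% and 20–21%. The AUCs in the synopsis (0.68, 0.69 and 0.66 with a biomarker, 0.67 without; p = 0.37, 0.32 and 0.09) also show no apparent biomarker gain for a stronger benchmark to remove.

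A reader might also infer that CEA was entered raw and lost a third or more of its information. The SAP gives no form for CEA in the model. The mean is a descriptive label, and the SAP also calls for medians, quartiles and rank-sum tests for continuous data. This is a gap in specification.

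Finally, AUC results are already in the SAP, so recoding now would reopen model choices after the results are known. That stands, and it governs how a re-run should be labelled.

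**Conclusion.** The point holds for age and LDH in the a priori adjusted Cox model, as a minor improvement. For age the loss is about 36% or more under normality and a linear effect, less under other shapes, and nil under a true step. For LDH the loss takes the same form, with a size that depends on the unreported share above 450 U/L. The residual bias in a biomarker hazard ratio is small beside sampling error, at most about 0.3 of a standard error in the settings tried, and it arises only if age differs between biomarker groups, which the documents neither state nor exclude. For CEA the finding is that its scale is missing. No effect on Score 1 or on the AUC comparison is shown; on the assumptions above it would be small.

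**What to change.** In SAP 6.5.1.5, enter age as continuous (per 10 years), LDH as continuous on a log scale and CEA as log2(CEA) in the adjusted model. Keep the cuts at 65 and 450 for display tables only. State the coding of all three in the univariate screen and use the same coding there. Label any re-run as a sensitivity analysis, because the AUC results are already reported.

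The cost is a change in the analysis program: no new data, and no extra degrees of freedom for age or LDH. Linearity on the chosen scale is assumed and should be checked. A score that came to include these terms would be slightly less simple to use. LDH is measured in local laboratories (Protocol 8.1), so differences in scale between sites may matter; the fixed 450 cut has the same weakness.

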	
quartiles were calculated according to Brookmeyer and Crowley methods (55,56). Safety data were analysed throughout the entire study.
 
In the first step to develop a prediction model for PFS, univariate Cox regression analysis including all clinical variables collected in the study was performed in order to identify which should be considered for the model selection thereafter in the second step. All factors with a ≤ 0.15 p value (Appendix 15.2, item 4) were selected for the multivariable Cox analysis. The cut-off of ≤ 0.15 p-value was used in order to include the presence of resectable liver metastases as that is a well-known prognostic factor in mCRC. In the second step multivariable Cox regression analysis was performed including those variables identified in the univariate analysis. Importantly, the variable treatment (FOLFIRI vs FOLFOX) was not included for the development of the prediction score because it was not a characteristic intrinsic to the patients.

--	--

12-MONTHS PFS RISK MODEL DEFINITION

Clinical variables and biomarkers were used to build a score to predict 12-months PFS, by using a multivariable Cox regression model built with those clinical variables with a $p \leq 0.15$ in the multivariable analysis (performance status, chemotherapy regimen, sidedness, resectable only liver metastases). Once the first risk score was built adding up the coefficients of the multivariable model ($PS > 0 = 0.6$, left sided = -0.5, resectable liver only metastases = -0.4 and folfiri+cetuximab therapy = Not evaluable), ROC curves were computed for PFS at 12 months using a logistic regression model. All 4 scores (A. Clinical variables including PS, sidedness and resectable only liver metastases, B. Clinical variables + BRAF mutation; C. Clinical variables + PI3K mutation or PTEN ≤ 3 ; D. Clinical variables + DP) had comparable low areas under the curve, ranging between 0.5 and 0.7, overall: The AUC of the score containing the clinical variables was 0.67 (95% CI) (0.60-0.75).

The AUC of the score with clinical variables and BRAF mutational status was 0.68 (0.61-0.75, p-value = 0.37). The AUC of the score with clinical variables and PI3KCA mutation/PTEN status was 0.69 (0.61-0.76, p-value = 0.32). The AUC of the score with clinical variables and DP phenotype was 0.66 (0.58-0.73, p-value = 0.09).

SAFETY RESULTS

CONCLUSIONS

DATE OF THE REPORT:

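### SAP 6.5.1.5 describes an a priori Cox model and a stepwise one for PFS and OS without saying how they combine, whether the biomarker is forced in, or which supplies the reported adjusted hazard ratio

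*SAP*

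**What the plan says.** SAP 6.5.1.5 gives the purpose of these models: "Cox proportional hazards regression with the Efron method for ties was used to identify prognostic factors for PFS and OS".

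It then gives two rules for one multivariable analysis.

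- **A priori rule.** "Multivariable analysis was performed using subject-matter knowledge and deciding a" priori which variables to use. The list is "the variables to adjust by age (>65 years), sex, tumour site (right vs left), surgery of primary tumour, liver only metastases" (with size and number limits), followed by "ECOG PS, LDH (>450 U/L) and CEA, BRAF mutational status, and type of therapy". That makes ten variables. BRAF is the only biomarker among them; DP and PI3K-PTEN are not mentioned.
- **Data-driven rule.** The next sentence reads "This analysis was later adjusted by variables with p-values <0.10 in the" univariate analysis, using automated stepwise selection with p-value limits of 0.2 to enter and 0.1 to stay.

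The section adds that p-values are two-sided and gives no multiplicity rule. In SAP section 7, the OS text that begins "The median OS of wt-BRAF patients was X" goes on to ask for one adjusted hazard ratio with interval and p-value for BRAF. It names no model. Protocol 10.4 does not settle the matter, since it says only that the classification will use the variables with most impact in the multivariate analysis.

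**The concern.** The two rules can produce different models, and the wording allows at least two ways of combining them. If the stepwise variables are added to the ten, the a priori adjustment survives and the model only grows. If they replace the ten, any named confounder, and BRAF itself, stays or leaves on a p-value computed from the same patients.

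Under replacement, three things follow for a biomarker in the primary objective. It may have no adjusted hazard ratio at all. When it has one, the estimate has passed a significance filter and so tends to be too large. The printed interval and p-value are calculated as though the model had been fixed in advance. Because the SAP does not say which fit is reported, the choice can be made after both results are known.

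**Working it through.** **Inputs.** 181 efficacy patients (SAP synopsis), 20 with mutant BRAF (SAP Table 6), 115 events (protocol 10.2.5, SAP 6.5.2), hazard ratio 1.79 (SAP 6.5.2), and the screen and stepwise limits of SAP 6.5.1.5.

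**1. The design figure.** SAP 6.5.1.5 has no figure of its own, so the check starts from the 115 events. Protocol 10.2.5 assumes 60% against 40% free of progression at 12 months:

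HR = ln(0.40)/ln(0.60) = 1.794.

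Freedman's formula with a 40:60 split, k = 1.5:

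events = (1.960 + 0.842)² × (1 + k·HR)² / [k·(HR − 1)²] = 7.849 × 13.62 / 0.945 = 113.1.

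That rounds up to 114, close to the stated 115. (The SAP's 50% against 30% gives ln(0.30)/ln(0.50) = 1.737, not 1.79. That is a separate matter; 1.79 is used here as an assumed true BRAF effect.)

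**2. Hand calculation of the p<0.10 screen.** Mutant share = 20/181 = 0.1105.

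- SE(log HR) ≈ 1/√(115 × 0.1105 × 0.8895) = 0.297.
- Expected z = ln(1.79)/0.297 = 0.582/0.297 = 1.957.
- Probability of passing = Φ(1.957 − 1.645) = Φ(0.312) = 62%, so about 38% fail.
- Smallest estimate that can pass = exp(1.645 × 0.297) = 1.63.
- Mean log HR among those passing = 0.582 + 0.297 × φ(0.312)/0.623 = 0.764, a hazard ratio of about 2.15.

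This approximation uses the baseline mutant share. With a hazard ratio above 1, mutant patients supply more than their share of events, so the true failure rate is somewhat lower.

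**3. Simulation, replacement reading.** 2,000 trials of 181 patients were each stopped at 115 events. There were nine binary covariates at 50% prevalence, plus BRAF at 20/181 with true HR 1.79. Latent correlation was 0.2, and the other covariates had no effect.

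- Stepwise kept BRAF in 66% of trials and dropped it in about 34%.
- With BRAF put back into the stepwise fit, its hazard ratio differed from the a priori one by a median factor of 1.06 (95th percentile 1.23). The two disagreed on p<0.05 in 9.7% of trials.

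Further runs (600 per scenario) gave 29-36% dropped, a hazard ratio of about 2.0-2.1 when kept, and disagreement in 10-12%. The a priori model always reported BRAF, with an average of about 1.9.

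**4. No true BRAF effect.** In a separate simulation (1,500 trials per scenario, 20 candidates), BRAF reached p<0.05 in 5.3% (a priori), 4.0% (stepwise) and 6.3% (either). The Monte Carlo standard error was about 0.6 points. The last figure rose to 8.5% only when BRAF was assumed to be linked to tumour side (60% against 25%).

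**5. Covariates with no effect.** With ten independent null variables, the chance of at least one p<0.05 is 1 − 0.95¹⁰ = 40%. The 2,000-trial simulation gave about 44% for the a priori model and 39-40% for stepwise. The further runs, under other assumptions, gave 28-32% and 16-23%. The a priori model is no better here.

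**The case against.** The strongest reply is that this is explanatory modelling in a single-arm phase II trial. SAP 6.5.1.1 makes the primary analysis a comparison of AUCs for a clinical score with and without each biomarker, and the score is built by its own steps. The visible shells ask for one adjusted hazard ratio, for BRAF on OS, while the simulations model PFS. The added-variables reading is as natural as replacement, and under it BRAF is never dropped. All of this stands and limits the reach of the point. It does not tell a reader which model produced the reported number.

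A reader might infer more than the documents support:

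- **That choosing between the models inflates the BRAF false-positive rate.** It barely does; the figures are 4-6% without an assumed association with side.
- **That a promised 5% family-wise error is broken.** The 5% in protocol 10.2.5 and SAP 6.5.2 is for one two-group log-rank comparison. No such promise covers covariates.
- **That the limit of 0.10 contradicts the 0.15 used elsewhere.** The synopsis, where "univariate Cox regression analysis including all clinical variables collected in the study was performed", presents 0.15 as a step in developing the prediction model. SAP 6.5.1.5 uses it for the score. These are separate analyses.
- **That the stepwise sentence should be struck out.** The SAP is in the past tense and records work done. Removing the sentence would hide an analysis rather than classify it.

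**Conclusion.** The point holds as a moderate one about the adjusted Cox results for PFS and OS. The plan does not determine which hazard ratio is reported, and one permitted reading lets a p-value decide whether a biomarker in the primary objective is reported at all.

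The sizes from the simulations depend on the replacement reading, a true hazard ratio of 1.79, 115 PFS events, 20 mutants in 181, and assumed covariate prevalences and correlations. The exaggeration is best judged against the a priori average of about 1.9: 2.0/1.9 = 1.05 to 2.1/1.9 = 1.11, so about 5-11% beyond what an unselected fit of this size shows. For OS the event count is not stated, so no matching figure can be given. The missing multiplicity rule is a real gap, but both models share it, and preferring one does not close it.

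**What to change.** In SAP 6.5.1.5:

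1. State that the a priori covariate set is the model that supplies every adjusted hazard ratio, 95% interval and p-value for PFS and OS, including those in section 7.
2. State that each biomarker (BRAF, PI3K-PTEN, DP) is forced in alongside the same clinical covariates.
3. Keep the stepwise fit as a sensitivity analysis labelled exploratory, with the biomarker and the a priori covariates forced in, so that selection can only add variables.
4. Label the p-values for covariates read as prognostic factors, from either model, as exploratory.

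The cost is one paragraph and a slightly wider interval from carrying about ten covariates. At 115 PFS events this leaves 115/10 = 11.5 events per covariate. The OS equivalent should be stated once the number of deaths is known.
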